6.1.8. Data Adjustments/Handling/Conventions

All collected data will be presented in listings. Data not subject to analysis according to this plan will not appear in any tables or graphs but will be included only in the data listings.

All *P* values will be displayed in four decimals and rounded using standard scientific notation (e.g., 0.XXXX). If a *P* value less than 0.0001 occurs it will be shown in tables as <0.0001.

Adverse events will be coded using the MedDRA version 21.0 thesaurus or higher.

A treatment related AE is any AE with a relationship to the study drug of possibly related or definitely related.

If partial AE or medication dates occur, the convention for replacing missing dates for the purpose of statistical analysis is as follows:

For partial AE and medication start dates:

- If the year is unknown, then do not impute the date but assign a missing value.
- If the year is known, but the month or month and day is unknown, then:
 - If the year matches the year of first dose date and the end date (if present) is after first dose date, then impute as the month and day of the first dose date.
 - Otherwise, assign 01 January.
- If the year and month are known, but the day is unknown, then:
 - If the month and year match the month and year of the first dose date, then impute as the day of the first dose date.
 - Otherwise, assign 01.

For partial AE and medication end dates:

- If the year is unknown, then do not impute the date but assign as missing value.
- If the year is known, but the month or month and day is unknown, then:
 - If the year matches the year of the last date of the study (date of last contact if subject lost to follow-up; date of completion or early termination otherwise), then impute as the month and day of the last date of the study.
 - Otherwise, assign 31 December.
- If the year and month are known, but the day is unknown, then:
 - If the month and year match the month and year of the last date of the study, then impute as the day of the last date of the study.
 - Otherwise, assign the last day of the month.

If partial times occur, the convention is as follows:

- if the missing time occurs on the day of the first dose and both the hour and minute are missing then the time assigned is the time of the first dose, otherwise if both the hour and minute are missing and the date is not the date of first dose the time assigned is 12:00;
- if the date is the same as the date of the first dose and
 - only hour is missing the hour assigned is 12 or the hour of first dose, whichever is later;
 - only the minute is missing the minute assigned is 30 or the minute of first dose, whichever is later;
- Otherwise if the date is not the same as the date of first dose, the hour assigned is 12 if the hour is missing and the minute assigned is 30 if the minute is missing.

7. Study Subjects and Demographics

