- PDQ-39 Emotional Well-Being subscore = sum of 6 items in the Emotional Well-Being domain (converted from a range of 0 [never] to 4 [always/cannot do at all] to a range of 0 to 100), divided by the maximum possible score on the scale and multiplied by 100.

- PDQ-39 Stigma subscore = sum of 4 items in the Stigma domain (converted from a range of 0 [never] to 4 [always/cannot do at all] to a range of 0 to 100), divided by the maximum possible score on the scale and multiplied by 100.
- PDQ-39 Social Support subscore = sum of 3 items in the Social Support domain (converted from a range of 0 [never] to 4 [always/cannot do at all] to a range of 0 to 100), divided by the maximum possible score on the scale and multiplied by 100.
- PDQ-39 Cognitions subscore = sum of 4 items in the Cognitions domain (converted from a range of 0 [never] to 4 [always/cannot do at all] to a range of 0 to 100), divided by the maximum possible score on the scale and multiplied by 100.
- PDQ-39 Communication subscore = sum of 3 items in the Communication domain (converted from a range of 0 [never] to 4 [always/cannot do at all] to a range of 0 to 100), divided by the maximum possible score on the scale and multiplied by 100.
- PDQ-39 Bodily Discomfort subscore = sum of 3 items in the Bodily Discomfort domain (converted from a range of 0 [never] to 4 [always/cannot do at all] to a range of 0 to 100), divided by the maximum possible score on the scale and multiplied by 100.
- PDQ-39 Total score = mean of all of the PDQ-39 subscores.
- GDS-15 Total score = sum of the 15 item questionnaire, with a range of 0 to 15. Each question is answered “yes” or “no”. Question numbers 1, 5, 7, 11, 13 indicate presence of depression when answered positively (yes) while the remaining questions indicate presence of depression when answered negatively (no). One point is counted for each depressive answer. A score of 0-4 indicates no depression, a score of 5-10 is suggestive of a mild depression, and a score of 11 or more is suggestive of severe depression.
- Modified Hachinski Ischemic Scale Total score = sum of the 8 item scores, with a range of 0-8.
- Change from baseline = value at current time point – value at baseline.
- TEAE = any adverse event with an onset date/time after first dose of medication.
- Disease duration (years) = [Enrollment date – PD onset date (as recorded on the Medical History case report form) + 1] / 365.25.

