9.1. Adverse Events

All AEs that occur after the time of treatment with the study agent will be considered TEAEs. Events meeting this definition will be those events that are a change from the subject's baseline conditions, including an increase in frequency or severity (these will be entered as new AEs). For AEs occurring on the date of first dose, if the time of onset is missing, the AE will be assumed to be treatment emergent.

All AEs, TEAEs, and SAEs will be coded using the MedDRA Version 20.1 or higher coding dictionary. The AE analyses will focus on those that are treatment emergent, however any AEs that are reported after consent has been signed and before initial dosing will be considered intercurrent events and flagged in the listings as such.

The causal relationship of the AE to the study drug is determined by the investigator as Unrelated, Possibly Related, or Definitely Related. These can be mapped to Unrelated (*Unrelated*) and Related (*Possibly Related* and *Definitely Related*). Adverse event summaries will be repeated for treatment related TEAEs.

Adverse events severity grades are reported as mild, moderate, or severe.

Summaries of incidence rates (frequencies and percentages) of individual TEAEs will be presented by SOC, PT, and treatment group. Such summaries will be displayed for all TEAEs, TEAEs by maximum severity, and TEAEs by relationship.

Each subject will be counted only once within each summation level (SOC and PT). If a subject experiences more than 1 TEAE within each summation level only, the TEAE with the strongest relationship or the maximum severity, as appropriate, will be included in the summaries of relationship and severity. If a particular event is missing the severity and/or relationship, then the strongest possible severity or relationship will be assumed for analysis (severity = severe, relationship = definitely related).

Incidences will be presented by descending frequency of SOC and PT within SOC, and then alphabetically within PT where the incidence is the same; this is based on overall subjects then alphabetically in case of a tie.

Missing and partially missing AE start and/or stop dates will be imputed, for the purpose of statistical analysis, according to the specifications described in Section 6.1.8.

In the AE data listings, all AEs will be displayed. AEs that are treatment emergent will be flagged.

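### When only the start day is unknown, the AE date rule omits the end-date check, so a resolved pre-dose AE can become a TEAE; TEAE status for an unknown start year is not defined

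*SAP*

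**What the plan says.** SAP 6.1.8 handles partial AE start dates in three branches.

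- Year unknown: "If the year is unknown, then do not impute the date but assign a missing value".
- Year known, month unknown: the first-dose month and day are used if the year matches first dose "and the end date (if present) is after first dose date"; otherwise 1 January is assigned.
- Year and month known, day unknown: if month and year match first dose, "then impute as the day of the first dose date"; otherwise day 01 is assigned. This branch does not mention the end date.

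For onset times on the day of first dose, SAP 6.1.8 adds that if "both the hour and minute are missing then the time assigned is the time of the first dose".

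TEAE status is then set in two places. SAP 6.1.7 defines a TEAE as "any adverse event with an onset date/time after first dose of medication". SAP 9.1 says that for an AE on the date of first dose, "if the time of onset is missing, the AE will be assumed to be treatment emergent". SAP 9.1 also sends AEs reported between consent and initial dosing to a separate intercurrent category, flagged in the listings.

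**The concern.** The more complete date gets the weaker check. If the month is missing, the end date can stop the first-dose date from being imputed. If the month is known and only the day is missing, nothing stops it, even where a recorded end date shows that the event was over before dosing. The result is a start later than the stop and, by way of SAP 9.1, a treatment-emergent classification for an event that cannot be one.

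A gap in the opposite direction arises when the start year is unknown. The onset stays missing, and a missing onset cannot be later than first dose. Elsewhere SAP 9.1 sets cautious defaults: missing severity becomes severe, missing relationship becomes definitely related, and missing onset time on the dosing day becomes treatment emergent. The footnote to the concomitant-medication shell (Table 14.3.6.4) classifies medications with no start date by their stop date. AEs have no equivalent.

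TEAE incidence is half of the primary endpoint (SAP 2.2.1.1), and SAP 9.1 tests it between arms. An ambiguous rule here could lead two programmers to different primary tables.

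**Working it through.** The plan attaches no figure to this rule, so there is nothing to reproduce. The check traces the rules through worked cases and then enumerates cases.

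**Inputs.** Imputation and time rules: SAP 6.1.8. TEAE definitions: SAP 6.1.7 and 9.1. Pre-dose window: screening opens on Day -35 (Protocol 4.1). Planned arm sizes: 60 active and 30 placebo (SAP 3.2).

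**Worked cases.** Take first dose on 20 June 2019 (an illustrative date), with no onset time recorded.

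| AE start as recorded | AE end | Imputed start | TEAE by 9.1 same-day default | TEAE by 6.1.7 |
|---|---|---|---|---|
| day unknown, June 2019 | 12 June 2019 | 20 June 2019 | yes | no |
| day and month unknown, 2019 | 12 June 2019 | 1 January 2019 | no | no |
| day unknown, June 2019 | 25 June 2019 | 20 June 2019 | yes | no |
| year unknown | not recorded | missing | no | no |

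- Row 1: the start falls 20 − 12 = 8 days after the stop. The imputed onset time equals the first-dose time, so the event is not strictly after first dose under 6.1.7, but 9.1 makes it a TEAE.
- Row 2: the same event with less information is correctly placed before dosing.
- Row 3: this event may truly be treatment emergent. The two definitions disagree here too, and 6.1.7 read alone would leave it out.
- Row 4: the event fails the literal definition only because no default exists.

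**Enumeration.** Take every first-dose date in 2019 (365), every AE start from 1 to 35 days before dosing, and every end from the start day to the day before dosing, with only the start day blanked.

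- Cases: 365 × (1 + 2 + … + 35) = 365 × 630 = 229,950.
- Day-unknown rule with the 9.1 default: 56,354 become TEAEs (56,354 / 229,950 = 24.5%), and all 56,354 have a start after the stop.
- Same cases with the month also blanked: 0 become TEAEs.
- Day-unknown rule with the month-unknown branch's end-date clause added: 0 become TEAEs and 0 have a start after the stop.

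The 24.5% is a share of equally weighted hypothetical cases. It shows that the fault is systematic within the rule; it is not an expected rate in the trial.

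**Size per subject.** 1/60 = 1.7 percentage points (active); 1/30 = 3.3 percentage points (placebo).

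**The case against.** **SAP 6.1.7 alone does not make the event a TEAE.** This is correct: the imputed onset coincides with first dose and is not after it. The misclassification needs the same-day default in 9.1. That corrects the route but leaves the problem, because the SAP then holds two definitions that give opposite answers for these records and does not say which governs.

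**The intercurrent-event rule competes.** It turns on when an AE is reported, not on its imputed onset. AEs are reviewed at Visit 2 (Protocol 7.3.3) and again before the first infusion at Visit 3 (Protocol 7.3.4), so an event that resolved before dosing should normally be known by then. This stands, and it narrows the exposure to late-reported events or to programming that lets the imputed date override. The SAP does not state the order of precedence, and the rule does nothing about the impossible start date.

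**Unknown-year AEs.** A reader might infer that the plan drops these from the primary endpoint. The documents do not support that. The SAP is silent on their TEAE status; SAEs, the other half of the endpoint, are tabulated in SAP 9.1.2 without a TEAE or start-date condition; and all AEs are listed. The case is also remote, since onset date is a required AE item (Protocol 8.4.1) and participation lasts about 7 months.

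**Medications.** The same date rules cover medications, so a reader might infer that a drug stopped before dosing could appear to have begun on study and remove its subject from the Complete Set. That cannot be asserted. The Complete Set is nested in the Per Protocol Set, whose eligibility exclusions (SAP Section 5) already remove subjects with recent changes in several of the relevant drug classes. SAP 9.6 also plans a review of prior and concomitant medications before database lock.

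**Conclusion.** The point holds in a narrow form. The day-unknown branch lacks a check that the SAP applies one branch earlier. The stated rules can therefore produce a start after the stop and, through the same-day default in 9.1, a false TEAE, while 6.1.7 and the intercurrent rule say otherwise. The missing default for an unknown start year is a separate gap in the TEAE counts only.

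The effect is probably small. A false TEAE needs a missing start day, a start month equal to the dosing month, a known end before first dose, and an intercurrent rule that does not prevail. The documents give no frequency for partial dates; that they are few is an assumption. Nothing suggests that the error would differ by arm.

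The 1.7 and 3.3 points are maxima, not a shift that every misclassified subject causes. SAP 9.1 counts each subject once per summation level, so the overall rate moves only if the subject has no other TEAE, and an SOC or preferred-term row moves only if the subject has no other TEAE in that row. They also assume that the Safety Set matches the planned 60 and 30.

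It merits correction before database lock because it concerns the primary safety tables and costs almost nothing to settle.

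**What to change.** Four edits to the SAP:

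1. **6.1.8, day-unknown branch.** Impute the first-dose day only if the end date is missing or falls on or after first dose; otherwise assign day 01. The month-unknown clause says after first dose. Every enumerated case ends before the dosing date, so either wording gives the zero counts shown above.
2. **6.1.8, general.** Never impute a start later than the recorded end date.
3. **6.1.7 and 9.1.** Use one TEAE rule for onset on the first-dose date with a missing or imputed time, and say whether the intercurrent-event rule takes precedence over an imputed onset.
4. **6.1.8 or 9.1.** Treat an AE with a fully missing start as treatment emergent unless its end date is before first dose.

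The cost is a few sentences and a few lines of code. Data collection and trial conduct do not change.

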7.1. Disposition of Subjects and Withdrawals

Disposition will include tabulations of the number of subjects randomized into each treatment group, the number of subjects who completed each series of infusions in Dosing Period 1 and Dosing Period 2, the number of subjects completing the study, tabulated reasons for discontinuation from the study, and number of subjects in each analysis dataset. The number of subjects completing each visit will also be presented, as will the number of subjects who did not complete the study per protocol due to COVID-19. A subject is considered to not have completed the study per protocol due to COVID-19 if they had any missing visits that affected treatment administration or collection of end of study efficacy assessments due to COVID-19. If a subject did not complete the study per protocol due to COVID-19, this category will supersede their study status on the study completion CRF page.

This summary will be based on the ITT Set.

7.2. Protocol Violations and Deviations

Protocol deviations will be listed.

7.3. Demographics and Other Baseline Characteristics

Summary statistics for age, sex, race, ethnicity, height, weight, disease duration, and apolipoprotein E (ApoE) genotype will be presented by treatment group using summary statistics or frequencies, as appropriate. See Section 6.1.7 for derivation of disease duration.

The means of continuous demographic variables will be tested using Wilcoxon rank-sum test and the proportions of categorical demographic variables will be tested using a Chi-square test or Fisher's Exact test, as appropriate, in order to evaluate the effectiveness of the randomization in producing homogeneous pre-treatment groups.

These analyses will be conducted for the ITT Set.

The number and percent of subjects reporting various medical histories grouped by MedDRA system organ class and preferred term, will be tabulated. Medical histories of Parkinson's disease will also be presented by SOC, PT, and lower level term (LLT). Subject and family medical history as well as tobacco smoking, alcohol, and illicit substance use will be listed. Social history and exercise level will also be listed.

7.4. Exposure

All subjects will receive 5 consecutive days of therapy at the beginning of Weeks 1 and 13. Thus, the cumulative duration of therapy for all subjects will be 10 exposure days. The duration of therapy for a subject to be considered evaluable is 5 exposure days. Exposure days and volume administered will be summarized by treatment group and dosing period. The proportion of subjects who are considered evaluable over both dosing periods will also be displayed.

8. Efficacy Analysis

All secondary endpoints will be summarized using the Evaluable, Per Protocol, and Complete Sets. All efficacy data, regardless of population, will be presented in data listings.

8.1. Primary Efficacy Analysis

Not applicable. The primary analysis for this study is safety.

8.2. Secondary Efficacy Analysis

Normality assumptions will be tested using the Anderson-Darling method. If the P value for the normality test is >0.05 the data will be considered normally distributed and will be analyzed as specified in subsequent sections. Otherwise, if the P value is ≤ 0.05 the data will be considered non-normal. If the data are non-normal, the Wilcoxon rank sum test will be used for comparisons between treatments and a non-parametric ANCOVA model will be run on the ranks. If the data is considered non-normal, the Wilcoxon signed rank test will be used to assess the within-subject changes.

8.2.1. Montreal Cognitive Assessment (MoCA)

The MoCA is a 1-page, 30-point test designed as a rapid screening instrument for mild cognitive dysfunction. The questionnaire assesses several different cognitive domains, including attention and concentration, executive functions, memory, language, visuospatial skills, conceptual thinking, calculations, and orientation. Higher scores indicate better cognitive function; the total possible score is 30 and a score of 26 or more is considered normal. Derivation for the MoCA total score is described in Section 6.1.7.

The MoCA will be collected at Screening (Visit 1), Week 4 (Visit 9), and Week 16 (Visit 17).

Change from baseline to study visit in the MoCA total score and individual domains will be summarized by treatment group. Boxplots of the MoCA total score will also be provided by treatment group and visit. A test of hypothesis comparing mean total scores between baseline and subsequent study visits will be conducted using a 2-sided paired t-test or Wilcoxon signed

rank test, as appropriate. The null hypothesis is that the change from baseline to subsequent visit is 0.

Additionally, the mean change from baseline in MoCA total score will be compared between treatment groups using an ANCOVA model with treatment, visit, and treatment by visit interaction as a main effects and baseline MoCA total score, age, and ApoE genotype as covariates.

8.2.2. Cognitive Drug Research Computerized Cognition Battery (CDR-CCB)

The CDR-CCB assesses both enhancement and impairment of human cognitive function. In this study, the following will be measured using the CDR-CCB system: Continuity and Power of Attention, Working Memory, and Episodic Memory. Subjects will have two CDR-CCB training sessions during the screening period to ensure adequate performance at the Baseline Visit (Visit 2). CDR-CCB will also be assessed at Week 1 (Visit 8), Week 4 (Visit 9), Week 8 (Visit 10), Week 13 (Visit 16), Week 16 (Visit 17), Week 20 (Visit 18), and Week 24 (Visit 19).

Please refer to the separate SAP for the analysis of the CDR-CCB.

8.2.3. Delis-Kaplan Executive Function Verbal Fluency (D-KEFS)

The D-KEFS Verbal Fluency Test has three conditions: Letter Fluency, Category Fluency, and Category Switching. In the Letter Fluency condition, subjects are asked to say as many words that start with a particular letter (e.g., F, A, S) as possible over three trials of 60 seconds. The Category Fluency condition requires subjects to say as many words belonging to a particular semantic category (e.g., animals, tools) as they can in two trials of 60 seconds. In the final condition, subjects are asked to switch between words belonging to two different semantic categories in one trial of 60 seconds (e.g., fruits and furniture). D-KEFs is measured at Baseline (Visit 2), Week 1 (Visit 8), Week 8 (Visit 10), Week 13 (Visit 16), and Week 20 (Visit 18).

The number of correct F, A, and S responses from 1-15, 16-30, 31-46, and 46-60 seconds will be presented by treatment group and visit. Change from baseline in total score will be presented by treatment group. Derivation for the D-KEFS Total score is described in Section 6.1.7. Boxplots of the D-KEFSs total score will also be provided by treatment group and visit. A test of hypothesis comparing mean scores between baseline and subsequent study visits will be conducted using a 2-sided paired t-test or Wilcoxon signed rank test, as appropriate. The null hypothesis is that the mean change from baseline to subsequent visit is 0.

Mean change from Baseline will be compared between treatment groups using an ANCOVA model with treatment, visit, and treatment by visit interaction as a main effects and baseline score, age, and ApoE genotype as covariates.

8.2.5. Schwab and England Activities of Daily Living Scale (SE-ADL)

The SE-ADL evaluates patients' perceptions of global functional capacity and dependence. Scoring is expressed in terms of percentage, in 10 steps from 100 to 0 (100%, normal status; 0%, bedridden with vegetative dysfunction), so that the lower the score, the worse the functional status. The scoring is as follows:

Scale for the SE-ADL Rating	Description
100%	Completely independent. Able to do all chores without slowness, difficulty, or impairment. Essentially normal. Unaware of any difficulty.
90%	Completely independent. Able to do all chores with some degree of slowness, difficulty and impairment. May take twice as long. Beginning to be aware of difficulty.
80%	Completely independent in most chores. Takes twice as long. Conscious of difficulty and slowing.
70%	Not completed independent. More difficulty with some chores. X3-4 as long in some. May spend a large part of the day with chores.
60%	Some dependency. Can do most chores, but exceedingly slowly and with much effort. Errors; some impossible.
50%	More dependent. Help with ½ of chores. Difficulty with everything.
40%	Very dependent. Can assist with all chores but few alone.
30%	With effort, now and then does a few chores alone or begins alone. Much help needed.
20%	Nothing alone. Can do some slight help with some chores. Severe invalid.
10%	Totally dependent, helpless. Complete invalid
0%	Vegetative functions such as swallowing, bladder and bowel functions are not functioning. Bedridden.

The SE-ADL is measured at Baseline (Visit 2), Week 8 (Visit 10), and Week 24 (Visit 19). The number and percentage of subjects falling in each category at each time point will be displayed by treatment group. A 2-sided Cochran-Mantel-Haenszel (CMH) test will be performed at the 5% significance level to determine whether there is a significant relationship between treatment group and level of independence.

